12.1 Sample size justification

A total of 250 female patients presenting to UAB for stereotactic biopsy will be randomly assigned as 1:1 ratio to Arm1 (n=125) with advancing the clip to the biopsy site and deploying, or Arm2 (n=125) with advancing the clip to the biopsy site and retracting 5 mm and then deploying. Our hypothesis is that retracting to clip 5 mm before clip deployment will decrease clip migration, e.g. only 20% or less of breast biopsy patients who will have significant migration (greater than 10 mm from the biopsy site) while advancing the clip to the biopsy site and deploying without retracting will have at least of 50% significant migration. This size of 125 in each arm will have 99.9% power to test 30% difference (20% vs 50%) or >90% power to test at least 20% difference in proportion of patients who will have significant migration using one-sided Fisher's Exact test at 5% significant level (Table 1).

Table 1 Statistical Power to Test Differences Between Two arms.

Significant migration in Arm1 (%)	Significant migration in Arm2 (%)	Type I error (%)	Power (%)
50	15	5	100
50	20	5	99.9
50	25	5	99.1
50	30	5	93.1
50	15	1	100
50	20	1	99.6
50	25	1	95.4
50	30	1	78.5

A sample size of 125 will also produce two-sided 95% confidence interval to estimate the mean distance of migration with 0.177 standard deviation to the limits for each arm. Patients enrollment is expected to be completed within one year.

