2. BACKGROUND AND RATIONALE

Clip placement after stereotactic biopsy in breast imaging procedures has been an important part of breast imaging for years. There have been numerous studies documenting clip migration, and it is now a well-known phenomenon. Numerous case reports describe varying locations of clips following biopsy, some being as much as 5 cm from the biopsy site. This creates a problem in both benign and malignant diagnoses. In the setting of a benign biopsy, a clip remains important to provide correlation with a biopsy finding and the original suspicious mammographic site. In malignant diagnoses, the implication is more significant as the clip provides the localization site for excision. Clip migration has been suspected as the cause of up to 60% margin positivity (vs 0% when localizing the biopsy site by using hematoma identification) in breast cancer cases.¹ Although there have been recommended methods of deployment, vacuuming of cavity, release of compression after biopsy, and first post-biopsy mammography positioning techniques, there has been no prospective study assessing technique of clip retraction prior to deployment. Our hypothesis is that retracting to clip 5 mm before clip deployment will help to decrease clip migration. This will help improved accuracy of biopsy site localization and in cases of malignancy, will allow for less complicated, better localized, and improved results of tumor targeting for surgical resection.

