3. OBJECTIVES

3.1 Primary Objective

To determine which method decreases clip migration better, retracting the clip deployment apparatus 5 mm before deployment or not retracting.

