9. BENEFITS

If our hypothesis is true that retracting the clip 5 mm before clip deployment will help to decrease clip migration, this will help improved accuracy of biopsy site localization and in cases of malignancy, will allow for less complicated, better localized, and improved results of tumor targeting for surgical resection. If the hypothesis does not hold true, than this method of clip deployment should no longer be used as it does nothing to improve clip migration.

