11. DATA AND IMAGE ANALYSIS

11.1 **Image Evaluation and Analysis:** Clip migration will be measured on the post-biopsy mammogram compared to the pre-biopsy mammography exam. Clip migration will be measured by the location of the clip with respect to the biopsy site on the immediate post-clip mammography images. While delayed clip migration has been found in case reports, the number of cases of this phenomenon is not felt to warrant additional mammography exams for this study.⁸ The millimeters of clip migration will be measured on the CC view and on the true lateral (ML or LM) views. Although migration usually only occurs in one plane, both planes will be reviewed and if there is migration in two planes, one component factor (Pythagorean Theorem as has been used on prior studies¹) will be calculated.

11.2 We will consider significant migration is anything greater than 10 mm from the biopsy site. The use of 10 mm has been documented on prior studies and will be considered as a differentiation point in this study between significant and nonsignificant movement. A further reason for the use of the 10 mm cut off is that at this institution, Savi Scout devices are commonly used for localization. This device is 12 mm long and can accurately be placed at a location bridging the biopsy site and biopsy clip. Any complications will be reported.

12. STATISTICAL CONSIDERATION:

This is a single-center prospective randomized study to assess two techniques of clip retraction prior to deployment and to determine which method decreases clip migration better,

retracting the clip deployment apparatus 5 mm before deployment or not retracting. This will help improved accuracy of biopsy site localization and in cases of malignancy, will allow for less complicated, better localized, and improved results of tumor targeting for surgical resection.

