13.2 Statistical analysis plan

The primary objective of the number and percentage of breast biopsy patients whose clip has greater than 10 mm from the biopsy site as significant clip migration will be estimated and two-sided 95% confidence interval will be calculated using the method of Clopper–Pearson interval for each arm separately. Fisher exact test will be used to examine if there is significant association between arms in proportion of significant clip migration. The average of distance of clip migration will be estimated with two-sided 95% CI for each arm separately using normal approximation. Two-group student t-test will be used to evaluate the mean difference in the distance of migration from the original biopsy site between arms.

Correlation between migration and breast densities (entirely fatty, scattered fibroglandular densities, heterogeneously dense, extremely dense), different approaches (lateral, medial, superior) to biopsy, if thinner or thicker breasts and age under procedure of retracted (arm2) vs nonretracted (arm1) will be evaluated in two ways for the secondary objectives. First, we will consider significant clip migration (yes, no) as binary outcome. Analysis of Variance method (ANOVA) will be used to compare age differences with controlling of procedures, and Cochran -Mantel-Haenszel Test will be

used to compare differences in categorical variables, e.g. breast density stratified by retracted (arm2) vs nonretracted (arm1). Logistic regression analysis will be explored to identify significant factors associated with clip migration. Odds ratio and two-sided 95% CI will be presented for each factor significantly contributed in the model. Second, we will consider distance of clip migration (mm) as continuous outcome. ANOVA will be used to evaluate the strength of association (beta coefficient in the regression model) and identify significant of factors associated with the distances of migration.

All analysis will be carried out with Statistical software SAS v9.4.

REFERENCES

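### The trial is powered on a one-sided test, but the primary objective asks which method is better and section 13.2 gives neither sidedness nor alpha for the primary test

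*Combined protocol and SAP*

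**What the plan says.** **Sample size (12.1).** With 125 patients per arm, the plan claims 99.9% power for 50% v 20%. For a smaller effect it claims ">90% power to test at least 20% difference in proportion of patients who will have significant migration using one-sided". The test it names is Fisher's, and the level in the text is 5%. Table 1 also lists a 1% level. The stated hypothesis has a direction: "Our hypothesis is that retracting to clip 5 mm before clip deployment will decrease clip migration". Section 2 says the same.

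**Objective (3.1).** "To determine which method decreases clip migration better, retracting the clip deployment apparatus 5 mm before deployment or not retracting". Section 12 repeats it: the trial is "to assess two techniques of clip retraction prior to deployment and to determine which method decreases clip migration better". Neither sentence has a direction.

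**Analysis (13.2).** "Fisher exact test will be used to examine if there is significant association between arms in proportion of significant clip migration". No sidedness and no significance level are given for this test. The two-sided 95% intervals in 13.2 are for the estimates in each arm and for odds ratios, not for the between-arm primary test.

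**Consequence (section 9).** If the hypothesis fails, "this method of clip deployment should no longer be used as it does nothing to improve clip migration". No separate consequence is given for retraction being worse.

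**The concern.** The objective has two possible answers: retraction is better, or no retraction is better. A one-sided test in favour of retraction can support only the first. The analysis section, which should fix the decision rule, uses the language of association and leaves the rule open, so an analyst working from 13.2 alone could run either version.

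Two things are at stake. The cut-off for a positive trial depends on sidedness, and an unstated choice on the primary test could be made after the data are seen. And if retraction turned out to increase migration, the powered test would allow no conclusion to that effect, although the objective asks for one.

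**Working it through.** **Inputs.** 125 per arm, Arm 1 at 50%, Arm 2 at 15%, 20%, 25% or 30%, and levels of 5% and 1%, all from 12.1 and Table 1.

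**Method.** For each pair (x1, x2) with 0 ≤ x1, x2 ≤ 125, compute the Fisher p-value conditional on the total t = x1 + x2:
- one-sided: P(X ≥ x1), with X hypergeometric (250 patients, t events, 125 in Arm 1);
- two-sided: the sum of the probabilities of all tables no more likely than the one observed.

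Power = Σ Bin(x1; 125, p1) × Bin(x2; 125, p2) over the pairs with p ≤ alpha, on the full 126 × 126 grid.

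**Step 1: the plan's figures, then the two-sided equivalents.**

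| Arm 1 v Arm 2 | Level | Plan | Exact one-sided | Exact two-sided |
|---|---|---|---|---|
| 50 v 15 | 5% | 100 | 100 | 100 |
| 50 v 20 | 5% | 99.9 | 99.96 | 99.88 |
| 50 v 25 | 5% | 99.1 | 99.15 | 98.06 |
| 50 v 30 | 5% | 93.1 | 93.48 | 87.62 |
| 50 v 15 | 1% | 100 | 99.99 | 99.97 |
| 50 v 20 | 1% | 99.6 | 99.59 | 99.16 |
| 50 v 25 | 1% | 95.4 | 95.51 | 92.54 |
| 50 v 30 | 1% | 78.5 | 78.68 | 70.77 |

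All eight rows reproduce one-sided within 0.4 points. The 50 v 30 row at 5%, and the 50 v 25 and 50 v 30 rows at 1%, do not reproduce two-sided. Table 1 is therefore a one-sided table, and correct as such.

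**Step 2: a 20-point difference at other Arm 1 rates, two-sided 5%.** 40 v 20: 91.9%; 45 v 25: 89.8%; 55 v 35: 86.5%; 60 v 40: 86.4%. The smallest reduction from 50% that has 90% power is 18.6 points one-sided and 20.7 points two-sided.

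**Step 3: the cut-off.** Take Arm 1 = 62/125 (49.6%), the count nearest below 50%.

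| Arm 2 events | One-sided p | Two-sided p |
|---|---|---|
| 45 (36.0%) | 0.0203 | 0.0406 |
| 46 (36.8%) | 0.0276 | 0.0552 |
| 48 (38.4%) | 0.0487 | 0.0974 |
| 49 (39.2%) | 0.0632 | 0.1265 |

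The one-sided test is positive at 48 or fewer, the two-sided at 45 or fewer, so 46 to 48 is positive under one reading only. The share of trials positive one-sided but not two-sided is 93.48 − 87.62 = 5.86, about 5.9%, at 50 v 30; 99.15 − 98.06 = 1.09, about 1.1%, at 50 v 25; and 99.96 − 99.88 = 0.08% at 50 v 20.

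**Step 4: the other direction.** Arm 1 = 62 and Arm 2 = 79 (63.2%) gives two-sided p = 0.041 against retraction; the one-sided p is 0.989. If the true rates were 30% in Arm 1 and 50% in Arm 2, the one-sided test would reject in about 3 trials in 10 million, against 87.6% two-sided.

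**Step 5: error rate.** With both arms at 50%, the chance of wrongly declaring retraction better is 4.4% one-sided. Two-sided it is 1.8%, half of a total size of 3.7%.

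**The case against.** The case against is reasonable. A one-sided 5% test of a directional hypothesis, stated in advance, is legitimate. Sections 2 and 12.1 both give the direction. The protocol and SAP are one document, 12.1 specifies the test completely, and 13.2 names the same test on the same endpoint and says nothing contrary, so 12.1 can be read as governing. Section 9 gives the same action whether retraction is useless or worse, so a formal finding of harm would change no decision the plan describes. A reversed result would also show in the per-arm intervals and the comparison of mean distance. In the main 50% v 20% scenario the choice hardly matters.

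Most of this stands. There is no arithmetic error, 13.2 does not contradict 12.1, and the practical effect is confined to differences near 20 points or to retraction being worse. What it does not remove is the mismatch. The objective, stated twice, asks which method is better, and the powered test has essentially no power for one of the two answers. Neither the per-arm intervals nor the mean comparison is the powered primary test. And a sample size paragraph is a weak place to hold the only statement of the primary decision rule when the analysis section is open to either reading.

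**Conclusion.** The concern holds and should be fixed. The objective (3.1 and section 12), the powered test (12.1) and the analysis text (13.2) do not specify one decision rule that answers the stated question. This is a problem of alignment, not of power.

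The size is modest. If the test is read as two-sided, the claim of more than 90% power for a 20-point difference falls to 87.6% at 50% v 30%, and to about 86% at Arm 1 rates of 55% to 60%; it still holds at 40% v 20%. At most about 6% of trials in the tabulated 5% scenarios would change verdict, and under 0.1% at 50% v 20%. The larger gap is qualitative: under the one-sided test, no result can establish that no retraction is better.

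These figures assume 125 evaluable patients per arm, the event rates in Table 1, and the probability-based definition of the two-sided Fisher p-value. The 46 to 48 window is specific to 62 events in Arm 1.

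**What to change.** **Preferred, because it answers 3.1 as written.** State in both 12.1 and 13.2 that the primary test is a two-sided Fisher exact test at the 5% level, and keep 250 patients.
- Restate Table 1 for 50 v 15, 20, 25 and 30: 100, 99.9, 98.1 and 87.6 at 5%; 100, 99.2, 92.5 and 70.8 at 1%.
- Replace the claim of more than 90% power for a 20-point difference with about 88% for 50% v 30% (about 86% at Arm 1 rates of 55% to 60%).

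The cost is wording in two sections and one table. Stated power at 50% v 30% falls by 93.1 − 87.6 = 5.5 points, or 5.9 from the exact one-sided value. The required observed difference rises from 62 v 48 (14/125 = 11.2 points) to 62 v 45 (17/125 = 13.6 points). No extra patients are needed. If the sponsor wants 90% at 50% v 30%, exact enumeration gives 133 per arm (266 in total).

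**Alternative, if the one-sided test is kept.** State in 13.2 that the test is one-sided at 5% in favour of retraction, and reword 3.1 and section 12 to ask whether retraction reduces significant migration. Table 1 then stands. There is no loss of power, but the trial gives up any conclusion that no retraction is better.

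Either way, fix the choice before outcomes are compared by arm.

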13.2 Statistical analysis plan

The primary objective of the number and percentage of breast biopsy patients whose clip has greater than 10 mm from the biopsy site as significant clip migration will be estimated and two-sided 95% confidence interval will be calculated using the method of Clopper–Pearson interval for each arm separately. Fisher exact test will be used to examine if there is significant association between arms in proportion of significant clip migration. The average of distance of clip migration will be estimated with two-sided 95% CI for each arm separately using normal approximation. Two-group student t-test will be used to evaluate the mean difference in the distance of migration from the original biopsy site between arms.

Correlation between migration and breast densities (entirely fatty, scattered fibroglandular densities, heterogeneously dense, extremely dense), different approaches (lateral, medial, superior) to biopsy, if thinner or thicker breasts and age under procedure of retracted (arm2) vs nonretracted (arm1) will be evaluated in two ways for the secondary objectives. First, we will consider significant clip migration (yes, no) as binary outcome. Analysis of Variance method (ANOVA) will be used to compare age differences with controlling of procedures, and Cochran -Mantel-Haenszel Test will be

used to compare differences in categorical variables, e.g. breast density stratified by retracted (arm2) vs nonretracted (arm1). Logistic regression analysis will be explored to identify significant factors associated with clip migration. Odds ratio and two-sided 95% CI will be presented for each factor significantly contributed in the model. Second, we will consider distance of clip migration (mm) as continuous outcome. ANOVA will be used to evaluate the strength of association (beta coefficient in the regression model) and identify significant of factors associated with the distances of migration.

All analysis will be carried out with Statistical software SAS v9.4.

REFERENCES

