3.2 Secondary Objectives

- 3.2.1** Compare different breast densities (entirely fatty, scattered fibroglandular densities, heterogeneously dense, extremely dense) and their impact on clip migration in both groups (retracted vs nonretracted).
- 3.2.2** Compare different approaches (lateral, medial, superior) to biopsy and evaluate if they have an impact on clip migration in both groups (retracted vs nonretracted).
- 3.2.3** Evaluate if thinner or thicker breasts result in more or less clip migration in both groups (retracted vs nonretracted).
- 3.2.4** Evaluate if patient's age correlates with more or less clip migration in both groups (retracted vs nonretracted).

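### The between-arm comparisons are valid but unadjusted; if density, approach, thickness and age predict migration, some precision is lost, mainly on distance

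*Combined protocol and SAP*

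**What the plan says.** The primary objective (section 3.1) is "To determine which method decreases clip migration better, retracting the clip deployment apparatus 5 mm before deployment or not retracting". Section 13.2 makes the proportion with migration above 10 mm the primary measure and states: "Fisher exact test will be used to examine if there is significant association between arms in proportion of significant clip migration". For distance from the biopsy site it states: "Two-group student t-test will be used to evaluate the mean difference" between arms. Neither comparison includes a covariate.

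Section 3.2 lists breast density (four categories), approach (three), breast thickness and age as secondary questions, for example "Evaluate if thinner or thicker breasts result in more or less clip migration". Section 13.2 analyses these factors by ANOVA, by a Cochran-Mantel-Haenszel test stratified by arm, and by logistic and linear models. The stated purpose is to find which factors are associated with migration. Odds ratios are to be shown only for factors that contribute significantly. No covariate-adjusted effect of retraction is defined.

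Section 12.1 gives a 1:1 allocation and names no stratification factor. It plans power for the proportion "using one-sided Fisher's Exact test at 5% significant level". Section 13.2 does not say whether the Fisher test is one-sided or two-sided.

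**The concern.** The trial needs four candidate prognostic factors for its secondary objectives but does not use them when estimating the effect of retraction. If they explain part of the variation in migration, that variation stays in the standard error of the arm difference. With no stratification mentioned, any chance imbalance in them also stays in the estimate. Adjustment needs no extra patients, and no data beyond what the secondary objectives require.

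At stake is the width of the confidence interval for the retraction effect. It matters most for distance, which has no power calculation, only a per-arm precision statement.

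**Working it through.** **Inputs.** From section 12.1: 125 per arm, one-sided 5% Fisher test, 50% v 20% as the planned contrast and 50% v 30% as the smaller one, and a per-arm half-width of 0.177 SD. From section 3.2: density has 4 levels (3 parameters), approach has 3 levels (2), thickness takes 1 and age 1, so 7 covariate parameters. Assumed, because the documents give neither: R-squared (share of within-arm variance explained) from 0 to 0.30, and an illustrative distance difference of 0.30 SD. No SD in mm is given, so distance results are in SD units.

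**1. The plan's own figures reproduce.** Exact one-sided Fisher power at 5% with 125 per arm is 99.96% for 50% v 20% (plan 99.9%), 99.15% for 50% v 25% (plan 99.1%) and 93.48% for 50% v 30% (plan 93.1%; a continuity-corrected approximation gives 93.12%). The per-arm half-width is t(0.975; 124)/√125 = 0.177 SD, as stated.

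**2. Distance: interval width.**

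- Unadjusted: t(0.975; 248) × √(2/125) = 1.9696 × 0.1265 = 0.249 SD.
- Adjusted: t(0.975; 241) × √(2/125) × √(1 − R²) × √(247/240). The last factor is the expected variance cost of fitting 7 covariates: (250 − 3)/(250 − 7 − 3) = 247/240 = 1.029, about 3%.
- Example, R² = 0.10: 1.9699 × 0.1265 × 0.9487 × 1.0145 = 0.240 SD.
- Equivalent patients: 250 / [(1 − R²) × 247/240].
- Break-even: 1 − R² = 240/247, so R² is about 0.03.

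**3. Distance: power.** Two-sided 5%, noncentral t, at the illustrative 0.30 SD.

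| Analysis | Half-width (SD) | Equivalent patients | Power at 0.30 SD |
|---|---|---|---|
| t-test | 0.249 | 250 | 65.6% |
| ANCOVA, R² = 0 | 0.253 | 243 | 64.4% |
| ANCOVA, R² = 0.10 | 0.240 | 270 | 69.0% |
| ANCOVA, R² = 0.20 | 0.226 | 304 | 74.0% |
| ANCOVA, R² = 0.30 | 0.211 | 347 | 79.5% |

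**4. Proportion above 10 mm.** At the planned 50% v 20%, exact Fisher power is 99.96% one-sided and 99.88% two-sided, so adjustment has nothing useful to add. At 50% v 30% it is 93.5% one-sided and 87.6% two-sided.

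The effect on precision was simulated with a latent normal outcome. R-squared is on the latent scale, and the risk difference is standardised from a logistic model with arm and the four factors. Compared with the unadjusted risk difference, the variance is about 2 to 3% higher at R² = 0 and roughly 4%, 11% and 16% lower at 0.10, 0.20 and 0.30. Separate simulations with different settings gave reductions of about 1 to 5%, 7 to 12% and 14 to 18%, so these are approximate.

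In interval terms at 50% v 30%, the unadjusted half-width is 1.96 × √[(0.25 + 0.21)/125] = 11.9 percentage points. Multiplying by √0.96, √0.89 and √0.84 gives about 11.6, 11.2 and 10.9 points.

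**The case against.** The strongest reply is that nothing here is an error. Unadjusted tests are valid under 1:1 randomisation, the primary comparison is planned at 99.9% power, and the documents give no evidence that the four factors explain anything. Section 3.2 sets out to evaluate whether they matter; it does not assert that they do. All of that stands, and it limits the point to efficiency.

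A reader might infer more than the documents support:

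- *That the primary comparison is short of power.* It is not at 50% v 20%. At 50% v 30%, section 12.1 claims ">90% power to test at least 20% difference in proportion of patients who will have significant migration" on a one-sided test, and that reproduces. The 87.6% figure applies only if the test is run two-sided, which section 13.2 leaves open. Moving from a two-sided Fisher test to an unadjusted risk-difference test already gives about 91%, so that part of any gain would not come from adjustment.
- *That the plan ignores these factors.* It analyses all four, with arm taken into account. What is missing is an adjusted effect of arm.
- *That adjustment is free.* Useless covariates cost about 3% of variance, and below an R-squared of about 0.03 adjustment does not help.
- *That thickness is available in mm.* The documents speak only of thinner or thicker breasts and do not say how thickness is recorded.

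The unknown R-squared does not remove the point, because the trade is uneven. For distance at 0.30 SD, the worst case loses about 1 percentage point of power (65.6% to 64.4%), and R-squared of 0.30 gains about 14 (65.6% to 79.5%).

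**Conclusion.** The point holds as a modest, low-cost efficiency improvement, mainly for distance. With R-squared between 0.10 and 0.30, the interval for the distance difference narrows by about 4 to 15%, equivalent to about 270 to 347 patients instead of 250. With R-squared of 0 it widens by 1.5%. For the primary proportion the benefit is a somewhat narrower interval, not a rescued comparison.

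This rests on an assumed R-squared range, on 7 covariate parameters, and on 250 analysed patients. It also assumes that the factors are unaffected by arm. That is clear for age and density. For approach it is supported by section 6, where the radiologist settles positioning before the procedure. For thickness it is reasonable, though the documents do not describe the measurement. The 0.30 SD difference is an illustration only.

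**What to change.** In section 13.2:

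- Keep the Fisher test as the primary test for migration above 10 mm, and state whether it is one-sided or two-sided.
- Make ANCOVA of distance on arm, density, approach, thickness (as recorded) and age the main distance comparison. Report the adjusted mean difference with its 95% CI, with the t-test as a supporting result.
- For migration above 10 mm, add as a supporting estimate the risk difference with 95% CI, standardised from a logistic model with arm and the same four factors. This also supplies a between-arm interval for the proportion, where the plan now names only per-arm intervals. Use the risk difference because a conditional odds ratio would not itself be more precise.
- Settle the covariate list before any data are seen, and do not select covariates by significance. The factor-finding models stay as secondary analyses.

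Cost: SAP wording and a few lines of SAS, with no extra patients and no data beyond those needed for the secondary objectives. The downside is about 3% more variance if the factors explain nothing.

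### The tests named for secondary objectives 3.2.1–3.2.4 combine the two arms, so if a within-arm question is meant they cannot say which arm carries a factor's effect; odds ratios are also promised only for significant factors

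*Combined protocol and SAP*

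**What the plan says.** Section 3.2 lists four secondary objectives: breast density, biopsy approach, breast thickness and age. All four end with the same phrase. For density the plan will compare the categories "and their impact on clip migration in both groups (retracted vs nonretracted"); for age it asks whether "age correlates with more or less clip migration in both groups (retracted vs nonretracted").

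Section 13.2 takes up the same wording: the factors, ending with "age under procedure of retracted (arm2) vs nonretracted (arm1) will be evaluated in two ways for the secondary objectives". The two ways are the binary outcome (migration beyond 10 mm) and the distance in mm.

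- **Binary outcome, categorical factors:** a CMH test, "used to compare differences in categorical variables, e.g. breast density stratified by retracted (arm2) vs nonretracted (arm1").
- **Binary outcome, age:** "Analysis of Variance method (ANOVA) will be used to compare age differences with controlling of procedures".
- **Binary outcome, model:** "Logistic regression analysis will be explored to identify significant factors associated with clip migration". Then "Odds ratio and two-sided 95% CI will be presented for each factor significantly contributed in the model".
- **Distance:** "ANOVA will be used to evaluate the strength of association (beta coefficient in the regression model").

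The terms of the logistic and distance models are not listed. Separate estimation by arm is specified in section 13.2 only for the migration proportion and the mean distance, not for any factor effect.

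**The concern.** If the objectives ask about each factor within each procedure group, a test that pools the association over the arms answers a different question. It can detect that density matters somewhere. It cannot say whether density matters with retraction, without it, or in opposite directions. The risk is that a combined result is later reported as an answer for each group.

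The reporting rule for odds ratios is a second, smaller matter. It concerns the binary outcome only. If estimates are shown only when significant, those shown are selected for being large, and the remaining factors are promised no interval. A reader then cannot tell a factor with no effect from one that was poorly estimated.

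**Working it through.** The documents give no figure for the secondary analyses, so there is none to reproduce.

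**Inputs from the plan (section 12.1).** 125 patients per arm; planning rates of migration beyond 10 mm of 50% in Arm 1 (no retraction) and 20% in Arm 2 (retraction).

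**Assumed.** The documents give no factor distributions. I take a two-level factor split evenly within each arm, with rates averaging 50% and 20%, and two-sided 5% tests.

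**1. What the combined analysis estimates.** With an even split and equal arms, the Mantel–Haenszel common odds ratio is the sum over arms of p₁(1−p₀), divided by the sum over arms of (1−p₁)p₀.

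| Rates by factor level, Arm 1 v Arm 2 | OR in Arm 1 | OR in Arm 2 | Common OR |
|---|---|---|---|
| 60/40 v 20/20 (effect in Arm 1 only) | 0.36/0.16 = 2.25 | 0.16/0.16 = 1.0 | (0.36+0.16)/(0.16+0.16) = 1.625 |
| 50/50 v 30/10 (effect in Arm 2 only) | 0.25/0.25 = 1.0 | 0.27/0.07 = 3.86 | (0.25+0.27)/(0.25+0.07) = 1.625 |
| 60/40 v 10/30 (opposite directions) | 2.25 | 0.07/0.27 = 0.26 | (0.36+0.07)/(0.16+0.27) = 1.0 |

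**2. How often the CMH test rejects.** Each arm contributes a weight of 62.5×62.5/125 = 31.25. In the first two rows the numerator is 31.25×0.20 = 6.25. The variance is 31.25×(0.5×0.5) + 31.25×(0.2×0.8) = 12.81, with root 3.58. So z = 6.25/3.58 = 1.746, and power is Φ(1.746−1.96) = 41.5%. The calculation is the same in both rows, because the statistic uses only the summed difference and the arm averages. Simulation (20,000 trials per case, groups of 63 and 62) gives 42.0% and 41.6%. In the third row the differences cancel: simulated CMH rejection is 4.4–4.6%, its null rate, while a factor-by-arm test rejects in about 95%.

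**3. Where the planned test is the better one.** If the effects share a direction (60/40 v 25/15), z = 31.25×(0.20+0.10)/3.58 = 2.62 and CMH power is Φ(2.62−1.96), about 75%. The interaction test rejects in about 6%.

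**4. The odds-ratio rule.** Take a true OR of 1.5 (log 0.405) in a model with arm and one factor. With a and b patients at the two levels in each arm, the log-OR variance in an arm is (1/a+1/b)/(p(1−p)), and the arms are combined by inverse variance.

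- *Even split:* variances 0.128 and 0.200, SE 0.279. Power is Φ(0.405/0.279−1.96), about 31%. No OR below exp(1.96×0.279) = 1.73 is significant. The median when significant is exp(0.405+1.02×0.279), about 2.0.
- *20% exposed (25 v 100):* variances 0.200 and 0.3125, SE 0.349. Power is about 21%, the threshold is exp(1.96×0.349) = 1.98, and the median when significant is exp(0.405+1.25×0.349), about 2.3.

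The multipliers 1.02 and 1.25 are the normal quantiles that leave half the power in the upper tail. Simulation agrees: 30% with median 2.03, and 22% with median 2.33. A five-term model (arm plus four factors, thickness made binary) gives 28.3% with median 2.12, and 21.8% with median 2.42. At a true OR of 2.5 the five-term medians are 2.68 and 2.92, so the inflation shrinks as the effect grows.

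**5. What per-arm analysis could deliver.** The half-width for a within-arm risk difference is 1.96×√(p₁q₁/a + p₀q₀/b), at 60/40 in Arm 1 and 20/20 in Arm 2.

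- *Groups 63/62:* 1.96×√(0.24/63+0.24/62) = 17.2 points, and 1.96×√(0.16/63+0.16/62) = 14.0 points.
- *Groups 12/113 (about 10% of an arm):* 29.2 and 23.8 points.

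Interaction power for 60/40 v 20/20 with an even split: variances 2/(62.5×0.24) = 0.133 and 2/(62.5×0.16) = 0.200, so z = 0.811/√0.333 = 1.405 and power is Φ(1.405−1.96) = 29%. Simulation gives 28.6%.

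**The case against.** The strongest reply is that the mismatch exists on one reading only. The only operational text is section 13.2, and its two explicit tests stratify by or control for procedure, so the plan's authors may have meant an overall association allowing for arm. On that reading objective and test agree, and a clarifying phrase settles the matter. This stands: it makes the point an ambiguity to resolve, not a proven error.

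It is also true that the first two scenarios were built to share a common odds ratio, so their equal rejection rates follow from what the test is. They illustrate what a combined test cannot separate; they do not predict what will happen. Nor would an interaction p-value alone say which arm carries an effect. Only the arm-specific estimates do that, and they are wide.

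On the odds-ratio rule, the logistic regression is described as exploratory, and promising estimates for significant factors does not forbid showing the others. That is fair, but the plan does not promise them either.

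Two stronger readings are tempting. A reader might infer that every secondary analysis is arm-adjusted and that interactions are ruled out. The text does not support this: adjustment for arm is stated only for the CMH test and the age ANOVA, and neither the logistic nor the distance model lists its terms, so an interaction is unspecified, not excluded. A reader might also infer that the CMH test is the wrong choice. It is a sound overall test, and the better one when effects share a direction.

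**Conclusion.** The point holds as a minor one about secondary objectives. Section 3.2 leaves open whether the question is within each arm or across arms. If it is within each arm, the tests named for the binary outcome cannot say where an effect lies, and nothing else prespecified can. In the illustrations, one-arm effects give a common OR of 1.625 with about 42% rejection whichever arm carries them, and opposite effects disappear (common OR 1.0, about 5% rejection).

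The odds-ratio rule is a problem on either reading: at a true OR of 1.5, roughly 22–30% of trials would find significance, with a median of about 2.0–2.4 when they do.

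These sizes rest on assumed factor distributions, on the plan's 50% and 20% rates, and on 125 evaluable patients per arm. The documents do not support concluding that the secondary objectives will certainly go unanswered, or that the primary comparison is affected.

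**What to change.** 1. Report the odds ratio and 95% CI for every factor in the logistic model, whatever its p-value.
2. Settle the question that 3.2.1–3.2.4 ask.
   - If it is across arms, reword the four objectives as adjusted for arm.
   - If it is within arms, keep the CMH test and arm-controlled ANOVA as overall tests. For each factor and both outcomes, add the estimate with 95% CI in each arm and one factor-by-arm term. Label these exploratory, with no multiplicity control.

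**Cost.** SAP wording and extra output from data already collected; sample size, procedures and the primary test do not change. On the within-arm option the added results describe and do not confirm. Per-arm risk differences carry half-widths of about 14–17 points with an even split, and up to about 24–29 points if a category holds 10% of an arm. Interaction power is about 29% for 60/40 v 20/20 with an even split, and lower when the split is uneven. Four factors and two outcomes make eight interaction tests. If these were independent, the chance of at least one false positive would be 1−0.95⁸ = 34%. Because the 10 mm outcome is a cut of the same distance, the tests are correlated, and an illustrative simulation (normal distances, independent factors assumed) puts it nearer 30%.
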